## **8.3 Health Economics Evaluation**

The within trial analysis will be from the perspective of the NHS and personal social services (PSS) and will determine the cost-effectiveness and the cost-utility of a personalised prehabilitation (PPCP) compared to best practice usual care (BPUC). The primary effectiveness measure for the cost-effectiveness analysis will be change in FACIT-F and for the cost-utility analysis will be quality-adjusted life year (QALY). To estimate QALYs, health-related quality of life will be measured at baseline, post each chemotherapy cycle and three-months after completion of final cycle using the EQ-5D-5L measure. Using the trapezoidal rule, responses to the EQ-5D-5L will be converted into health utilities using the most appropriate utility algorithm as recommended by NICE [15]. The resource use questionnaire booklet will collect information on prehabilitation usage (including staff training, follow-up phone calls, weekly check-ins etc), specialist referrals, hospital admissions including readmissions and ICU admissions, number of transfusions, GP visits, complications of HSCT, and adverse events. This booklet will be first administered prior to cycle 2, and will collect the resource use data from baseline up until EOT. Unit costs will be estimated from local and national reference costs and reflatd to current prices and will be applied to each resource item to value total resource use in each arm of the trial. These costs and outcomes will be aligned with the NICE-reference case using bivariate regression of costs and outcomes which will inform a probabilistic assessment of incremental cost-effectiveness including 95% confidence intervals around mean cost and QALY differences between the trial groups. The incremental cost-effectiveness ratios (ICERs) will be expressed as cost per improvement in FACIT-F and cost per QALY gained. Results will be shown on a cost-effectiveness plane and plotted as cost-effectiveness acceptability curves. Sensitivity analyses will be undertaken to explore cost-effectiveness uncertainty and generalisability. As part of the sensitivity analyses, using a societal perspective we will look at the broader implications of costs and benefits associated with the personalised plan to patients and their families.

If there are differences between the two arms, modelling will be undertaken to estimate the longer-term costs and benefits of the PPCP compared with BPUC. The model type and time horizon are still to be decided. The model will be populated using data from the trial, published literature and expert opinion. Any future costs and benefits will be discounted at 3.5%.

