### 2.2.2 Secondary Outcomes:

- Emotional wellbeing: the Warwick-Edinburgh Mental Wellbeing Scale (WEMWBS) assesses participant's mental wellbeing and consists of 14 items, scored on a 5-point Likert scale score, giving an overall score [12].
- Anxiety and Depression: Patient Health Questionnaire 9-item (PHQ9) measures severity of depression and response to treatment. General Anxiety Disorder 7-item (GAD7) assesses the likelihood of the presence of the four most common clinical anxiety disorders [13, 14].
- Health-related quality of life:
  - FACIT F incorporates the 27 item FACT-G (Functional Assessment of Cancer Therapy – General) and measures four domains of health-related quality of life: physical, social, emotional and functional well-being.
  - EQ-5D-5L measures health status in 5 dimensions plus a visual analogue scale of self-rated health status [15].
- Physical function:
  - Performance Status: the Karnofsky Performance Scale Index allows patients to be classified as to their functional impairment, used in (p)rehabilitation [16].
  - The 6-minute walk test [17].
  - Hand grip strength [18].
- Incidence of sarcopenia: SARC-F [19]; calf circumference [20].
- Incidence of malnutrition: Utilising Malnutrition Universal Screening Tool (MUST) [21] and its determinants; % weight change, Body Mass Index (BMI), energy and protein intake (food diaries via myfood24) [22].
- Completion of consolidation treatment plan (chemotherapy +/- HSCT)
- Number of onward referrals to local services for 'specialist' therapies.
- Overall and relapse-free survival.
- Readmissions to hospital, ICU admission, number of transfusions, complications of HSCT, adverse events and serious adverse events.
- Costs, cost-effectiveness and utility: costs, health resource use and EQ-5D-5L.
- Process Evaluation: fidelity to intervention delivery and dose of intervention received for each component.
- Mechanisms of Action:
  - Psychological flexibility – is the mechanism of action for ACT, and the model within which all intervention methods are delivered. This will be measured with a shortened version (8-items) of the CompACT questionnaires [23]
  - Motivation – measured using 1-item from the COMB-Q adapted for each component (3-items total) [24].

All questionnaires being used for the patient reported outcomes have been previously validated or have been adapted from validated questionnaires to fit this specific context and patient group.

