## 4.9 Schedule of assessments

Visit	1	2	3	4	5	6	7	8
		Consolidation Treatment: To mirror the participant's planned treatment pathway						
Visit Window (No. Weeks ± No. Days)	Baseline*	Cycle 1 (Day 0) -8days	Cycle 2/HSCT -8days	Cycle 3/ HSCT -8days	EOT	3months post EOT	Month 24 (post randomisation anniversary)	Annual follow up (up to 5 years) (post randomisation anniversary)
Informed consent	x							
Medical history	x							
Confirm patient eligibility	x							
Randomisation		x a						
BPUC only: 30minute BPUC appointment		x						
PPCP only: MDT care planning sessions		x	x	x				
PPCP only: Participant check in		x Weekly check in						
Questionnaire booklet	x		x	x	x	x	x	
Health resource use questionnaire			x	x	x	x	x	

Visit	1	2	3	4	5	6	7	8
		Consolidation Treatment: To mirror the participant's planned treatment pathway						
Visit Window (No. Weeks ± No. Days)	Baseline*	Cycle 1 (Day 0) -8days	Cycle 2/HSCT -8days	Cycle 3/ HSCT -8days	EOT	3months post EOT	Month 24 (post randomisation anniversary)	Annual follow up (up to 5 years) (post randomisation anniversary)
PPCP only: Clinical screening questionnaire booklet		x	x	x				
6minute Walk Test	x					x b	x b	
Performance status	x	x	x	x	x	x	x	
SARC-F & Calf circumference	x				x b	x b	x b	
Hand grip strength	x				x b	x b	x b	
Height	x							
Weight	x	x c	x	x	x	x	x	
Food diary e	x d	x ce	x e	x e	x e	x e		
Haematology and biochemistry f	x f	x cf PPCP only	x f PPCP only	x f PPCP only				
Adverse events / complications of treatment			x	x	x			

Visit	1	2	3	4	5	6	7	8
		Consolidation Treatment: To mirror the participant's planned treatment pathway						
Visit Window (No. Weeks ± No. Days)	Baseline*	Cycle 1 (Day 0) -8days	Cycle 2/HSCT -8days	Cycle 3/ HSCT -8days	EOT	3months post EOT	Month 24 (post randomisation anniversary)	Annual follow up (up to 5 years) (post randomisation anniversary)
Review participant logbook			x g PPCP only	x g PPCP only	x g PPCP only			
Onward referrals		x As required h						
Survival status						x	x	x

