#### **4.10 Follow-up assessments**

To limit the burden on participants, only primary outcome and key secondary outcome data will be collected prior to each cycle of chemotherapy and at end of treatment (EOT). EOT within the PROPEL trial will be defined as following blood count recovery after the final cycle of intensive consolidation treatment (either chemotherapy or HSCT), where possible prior to discharge or at the EOT clinic review. Primary and secondary outcomes will be assessed in person at 3 months follow up post end of treatment (either chemotherapy or HSCT) and at 24 months post randomisation. Follow-up data for relapse and death will be collected up to 5 years from trial entry.

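### Section 8.3 stops resource-use collection at end of treatment but runs QALYs three months further, contradicting the protocol's own schedule and giving the ICER mismatched windows

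*Protocol*

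**What the plan says.** Section 8.3 sets the two sides of the economic comparison separately.

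- **QALYs:** "health-related quality of life will be measured at baseline, post each chemotherapy cycle and three-months after completion of final cycle using the EQ-5D-5L measure".
- **Costs:** the booklet is first given before cycle 2 and "will collect the resource use data from baseline up until EOT".
- **Combination:** "These costs and outcomes will be aligned with the NICE-reference case using bivariate regression of costs and outcomes", and the resulting ratios "will be expressed as cost per improvement in FACIT-F and cost per QALY gained".

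No 24-month point appears in the section.

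The schedule in section 4.9 differs. The row "Health resource use questionnaire" is marked at cycle 2/HSCT, cycle 3/HSCT, EOT, three months post EOT and month 24. The row "Questionnaire booklet" is marked at the same visits plus baseline. Section 4.10 agrees with the schedule (the closing figure in this quote counts months from randomisation): "Primary and secondary outcomes will be assessed in person at 3 months follow up post end of treatment (either chemotherapy or HSCT) and at 24". Section 2.2.2 counts the economic measures among the secondary outcomes: "Costs, cost-effectiveness and utility: costs, health resource use and EQ-5D-5L".

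Section 4.10 defines EOT by an event, count recovery after the last intensive consolidation treatment, and not by a fixed time from randomisation.

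**The concern.** A cost-per-QALY ratio needs costs and health effects counted over the same period. If the booklet stops at EOT, a readmission or HSCT complication in the following three months adds no booklet cost, while its effect on utility still counts. Section 8.3 names readmissions, ICU admissions and HSCT complications as cost items, so these are costs the analysis intends to capture.

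The end of both windows is also tied to EOT. The Trial Summary says treatment duration varies with the number of cycles and with HSCT. Section 2.1.2 compares completed cycles between arms, and section 1.2 hopes prehabilitation will help patients complete treatment. The length of the counting window could therefore depend on allocation.

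**Working it through.** The protocol gives no economic figure to reproduce, so the check compares the windows and then sizes the gap.

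**Windows**

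| Source | Costs end | EQ-5D-5L ends |
|---|---|---|
| Section 8.3 | EOT | three months after final cycle |
| Sections 4.9 and 4.10 | month 24 | month 24 |

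Two readings are used. The final cycle in 8.3 is taken to include HSCT, as in section 4.10, so that its end coincides with EOT. EQ-5D-5L is taken to be in the questionnaire booklet, which follows from sections 2.2.2 and 4.10 but is not stated in the schedule.

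**Uncosted share of the QALY window**

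Inputs from section 1.1: c = 2-3 consolidation cycles, L = 4-6 weeks per cycle, g = 1-2 weeks between cycles. Three months = 13 weeks.

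Weeks from start of consolidation to EOT = c × L + (c − 1) × g. Uncosted share = 13 / (EOT + 13).

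- Shortest: 2 × 4 + 1 × 1 = 9 weeks; 13 / 22 = 59%.
- Longest without HSCT: 3 × 6 + 2 × 2 = 22 weeks; 13 / 35 = 37%.
- HSCT assumed to count as a fourth cycle, longest: 4 × 6 + 3 × 2 = 30 weeks; 13 / 43 = 30%. The shortest such path is 4 × 4 + 3 × 1 = 19 weeks; 13 / 32 = 41%.

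The clock here starts at consolidation. Randomisation should come at least 8 days (8/7 = 1.1 weeks) earlier. Adding 1.1 weeks moves the non-HSCT range only to 13 / 36.1 = 36% and 13 / 23.1 = 56%.

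**Window length and arm**

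One extra cycle adds 4 + 1 = 5 to 6 + 2 = 8 weeks. Assume, for illustration only, that 10% more participants in one arm have one extra cycle, and that utility is 0.5-0.8 (neither figure is in the protocol).

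- Low: 0.10 × 5/52 × 0.5 = 0.005 QALY per patient.
- High: 0.10 × 8/52 × 0.8 = 0.012 QALY per patient.

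This difference comes from counting time alone. Costs would also accrue over those extra weeks.

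**Feasibility of 24 months for everyone**

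Set-up of 6 months plus 30 months of recruitment ends at month 36. Adding 24 months gives month 60, the end of the grant. The last EQ-5D-5L point before month 24 falls at 22-35 weeks without HSCT, so the next interval is 104 − 35 = 69 to 104 − 22 = 82 weeks.

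**The case against.** The strongest reply is that this is a conflict of wording. Section 8.3 describes what a booklet collects and never formally sets a costing horizon. It also speaks of valuing all resource use in each arm, and the schedule shows the same form collected later. That is fair as far as it goes: no scheduled data are lost, and aligning the text with the schedule removes the mismatch. But 8.3 names only the booklet as its resource-use source and gives it an explicit stop, so an analyst following 8.3 would produce unequal windows.

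Two possible repairs within the protocol do not suffice. The longer-term model in 8.3 is conditional on the arms differing and has no horizon yet. Treatment CRFs record treatment-related events (sections 6.1 and 6.2), but 8.3 does not cite them as a costing source.

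A reader might infer more than the documents support:

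- **That HSCT complications go uncosted altogether.** EOT follows count recovery after HSCT, so complications up to then fall inside the cost window. Only later ones fall outside.
- **That the uncosted share is 3 of 9 months, from the 6-month total in section 1.1.** That total appears to include induction, whereas baseline follows induction. The cycle ranges are the better basis.
- **That the ratio favours PPCP.** Uncosted events could fall in either arm, and a longer window adds costs as well as QALYs.
- **That a 24-month base case is required.** Not using month-24 data in the within-trial ratio is not in itself an error. The long EQ-5D-5L interval and the grant timetable make that horizon a trade-off.

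**Conclusion.** The point holds. Sections 8.3 and 4.9 contradict each other on when resource-use collection ends. Followed as written, 8.3 sets QALYs to three months post EOT against booklet costs to EOT. The uncosted 13 weeks are about 37% to 59% of the QALY window for 2-3 cycles, and about 30% on the longest assumed HSCT path. These shares rest on the cycle ranges in section 1.1 and measure time, not money. The effect on the ICER cannot be sized because the protocol gives no costs or utilities, and its direction is unknown.

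The possible dependence of window length on arm is a second, smaller issue. The 0.005-0.012 QALY figure illustrates it under assumed inputs and does not estimate a bias. Severity is moderate: cost-effectiveness is part of the stated aim, but the primary outcome, its power and the randomisation are untouched.

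**What to change.** Reword section 8.3 so that costs and QALYs share one stated window and agree with section 4.9. At minimum, replace the EOT stop for resource use with the three-month post-EOT form already in the schedule. This needs no new data collection, only a change to 8.3 and to any health-economics plan that follows it.

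That alone leaves the window specific to each participant. Add, as a secondary or sensitivity analysis, costs and QALYs over a common fixed time from randomisation using the scheduled month-24 forms, with second-year values discounted at the 3.5% that 8.3 already names for future costs and benefits. State its drawbacks: a long interval between EQ-5D-5L points, longer recall of resource use, more missing data, and the last recruits reaching month 24 as the grant ends.

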## **9 TRIAL ORGANISATION AND OVERSIGHT**

### **9.1 Sponsor and governance arrangements**

University Hospitals Coventry and Warwickshire (UHCW) and University of Warwick (UoW) will act as co-sponsors. The trial will be conducted in accordance with the principles and guidelines of the International Conference on Harmonisation (ICH), Good Clinical Practice (GCP) [53], UK legislation, WCTU SOPs and the Protocol. GCP-trained personnel will conduct the trial.

### **9.2 Ethical approval**

#### **9.2.1 Approvals**

All required ethical approval(s) for the trial will be sought using the Integrated Research Application System. The trial will be conducted in accordance with all relevant regulations.

Before enrolling patients into the trial, each trial site must ensure that the local conduct of the trial has the agreement of the relevant NHS Trust Research & Development (R&D) department. Sites will not be permitted to enrol patients into the trial until written confirmation of Capacity and Capability (CC&C) is received by WCTU and UHCW.

#### **9.2.2 Amendments**

All amendments will be documented by the PROPEL Trial Office. Substantial amendments will be submitted for HRA Approval, which includes NHS REC review, prior to communication to relevant participating NHS Organisations. Non-substantial amendments will be submitted to the HRA, and the applicable national coordinating functions in the devolved administrations, for review. Each trial site must ensure that they are using the most up to date version of the protocol, the Patient Information Sheet and Consent Form. All previous versions of the protocol, and other trial documents should be crossed out and marked as 'superseded', initialled and dated on the cover page.

#### **9.2.3 Annual Reports**

PROPEL Trial staff will send an annual trial update report to the NHS REC within 30 days of the anniversary date on which favourable opinion was given. This will be distributed to the local research team at each trial site. It is the responsibility of the local research team at each site to send a copy of this report to the research management function (e.g., R&D Office) in accordance with local requirements and recommendations made by the NHS REC. Any additional local information required must also be submitted. Additional data required by NHS Trusts is available from the PROPEL Trial Office on request.

NHS REC will be notified at the end of the trial, either at the planned end of study or prematurely. NHS REC will be notified within in writing within 15 days if the trial has been concluded or terminated early.

The CI will submit a final report to NHS REC with the results and any study publications within one year of the end of trial.

#### 9.2.4 Peer review

This study has been independently peer reviewed as part of the NIHR’s HTA application process.

### 9.3 Trial Registration

PROPEL is registered with the International Standard Randomised Controlled Trial Number (ISRCTN) Register: 17655532

### 9.4 Notification of serious breaches to GCP and/or trial protocol

A “serious breach” is a departure from the protocol, Sponsor procedures (i.e. SOPs), or regulatory requirements which is likely to effect to a significant degree –

- (a) The safety or physical or mental integrity of the subjects of the study; or
- (b) The scientific value of the study.

If a serious breach is confirmed by clear and unequivocal evidence, the study Sponsor must notify the REC within 7 days of the matter coming to their attention. The Corrective and Preventative Actions Report template, supplied by WCTU, may be used for this purpose.

### 9.5 Indemnity

NHS indemnity covers NHS staff, medical academic staff with honorary contracts, and those conducting the trial. NHS bodies carry this risk themselves or spread it through the Clinical Negligence Scheme for Trusts, which provides unlimited cover for this risk. The University of Warwick provides indemnity for any harm caused to participants by the design of the research protocol.

### 9.6 Trial timetable and milestones

Month	1-6	7-18	19-24	24-36	37-53	54-60
Grant activation						
Trial set up: protocol development						
Approvals						
Internal pilot						
Patient recruitment						
Data collection						

Patient follow-up						
Data cleaning						
Annual DMC/TSC meetings						
Data analysis						
Dissemination						
Trial close down						

## 9.7 Trial Management Group (TMG)

The Trial Management Group, consisting of the project staff and co-investigators involved in the day-to-day running of the trial, will meet regularly throughout the project. Significant issues arising from management meetings will be referred to the Trial Steering Committee or Investigators, as appropriate.

## 9.8 Trial Steering Committee (TSC)

The trial will be guided by a group of respected and experienced personnel and trialists as well as at least one 'lay' representative. The TSC will have an independent Chairperson. Face to face meetings will be held at regular intervals determined by need but not less than once a year. Routine business is conducted by email, post or teleconferencing.

The Steering Committee, in the development of this protocol and throughout the trial will take responsibility for:

- Major decisions such as a need to change the protocol for any reason
- Monitoring and supervising the progress of the trial
- Reviewing relevant information from other sources
- Considering recommendations from the DMC
- Informing and advising on all aspects of the trial

The full remit and responsibilities of the TSC will be documented in the Committee Charter which will be signed by all members.

## 9.9 Data Monitoring Committee (DMC)

An Independent Data Monitoring Committee (DMC) will be established for this trial.

DMC meetings will also be attended by the Chief Investigator(s) and Trial Co-ordinator (for non-confidential parts of the meeting) and the trial statistician.

The full remit and responsibilities of the DMC will be documented in the Committee Charter which will be signed by all members. The trial will meet prior to commencement and then annually thereafter or more frequently if requested. The DMC will review the main trial for trial progress, recruitment, protocol compliance and interim assessment of outcomes, annually or more frequently if requested. The DMC will advise the TSC whether the trial should continue, be amended or stop prematurely based on the trial data monitored and any future publications or emerging worldwide evidence.

### **9.10 Essential Documentation**

A Trial Master File will be set up according to Warwick SOP and held securely at the coordinating centre.

The coordinating centre will provide Investigator Site Files to all recruiting centres involved in the trial.

### **9.11 Financial Support**

This project is funded by the National Institute for Health Research's Health Technology Assessment programme, project number: NIHR134257. The views expressed are those of the author(s) and not necessarily those of the NIHR or the Department of Health and Social Care.

### **9.12 Ethical considerations**

The trial will be conducted in full conformance with Good Clinical Practice (GCP) guidelines [53] and the principles of the Declaration of Helsinki [54] . It will also comply with all applicable UK legislation and Warwick Standard Operating Procedures (SOPs). All data will be stored securely and held in accordance with the GDPR.HRA approval will be obtained, and the trial will be run in accordance with the UK Policy Framework for Health and Social Care Research; GDPR and the University of Warwick Sponsor and Quality Management system.

Sites will recruit patients once written confirmation of sites capacity and capability is received by WCTU and UHCW. Eligible patients will receive a patient information sheet and will be recruited after they have given informed consent. Consent to use their data for further research (optional) will also be requested and fully explained in the patient information.

## **10 MONITORING, AUDIT, AND INSPECTION**

A Trial Monitoring Plan will be developed and agreed by the TMG and TSC based on the trial risk assessment. It is anticipated that monitoring activity will be predominantly central and remote.

The Investigator(s) must ensure that source documents and other documentation for this study are made available to study monitors, the Research Ethics Committee (REC) or

equivalent local regulatory bodies for international centres. Authorised representatives of the Sponsor may visit the participating sites to conduct audits/ inspections.

All forms will be checked for completeness and consistency and any anomalies will be queried with the site. The trial staff will maintain regular communication with sites through routine calls, mailings and meetings. In the event of persistent issues with the quality and /or quantity of data submitted, an on-site monitoring visit may be arranged. In such circumstances, patient notes and the investigator site file must be available during the visit. A representative from the Trial Office will work with the site staff to resolve issues, offer appropriate training if necessary, and to determine the site's future participation in the trial.

